4.2.4.5 Forced expiratory volume in 1 second (FEV₁)

FEV₁ is measured at each clinical visit. FEV₁ will be analysed at each visit longitudinally separately for FEV₁ pre-dose/pre-BD and FEV₁ pre-dose/post-BD, using the same method, MMRM as described in [Section 4.2.4.2](#).

*FEV_{ijk} = Treatment group_i + baseline FEV_{1k} + visit_j + treatment_j*visit_j + random patient effect_k + covariates_k*; (where i =treatment group, j =visit and k =patient.)

The pre-dose/pre-BD baseline FEV₁ covariate will be used in the pre-dose/pre-BD model. The pre-dose/post-BD baseline FEV₁ covariate will be used in the pre-dose/post-BD model. Results will be presented for each timepoint and overall in terms of LSMEANS, treatment differences in LSMEANS, 95% confidence intervals and p-values.

The assumptions underlying the statistical model will be explored. If assumptions do not hold, then alternative strategies will be considered as described in [Section 4.2.4.2](#).

Summary statistics will be presented for each treatment group at each visit for pre-dose/pre-BD FEV₁ and pre-dose/post-BD FEV₁. The absolute score at each planned visit by treatment group, together with the corresponding changes from baseline will be summarised. Summaries will be descriptive statistics including N, mean, SD, median and range.

4.2.4.6 Peak expiratory flow (PEF)

PEF is measured daily using the ePRO device. For the purposes of summary and analysis, a weekly average PEF will be computed.

Weekly average PEF will be analysed longitudinally, using MMRM as described in [Section 4.2.4.2](#).

*Weekly average in PEF_{ijk} = Treatment group_i + baseline PEF_k + week_j + treatment_i*week_j + random patient effect_k + covariates_k; (where i=treatment group, j=week and k=patient).*

Results will be presented for each timepoint and overall in terms of LSMEANS, treatment differences in LSMEANS, 95% CI and p-values.

The assumptions underlying the statistical model will be explored. If assumptions do not hold, then alternative strategies will be considered as described in [Section 4.2.4.2](#).

Summary statistics for PEF will be produced by treatment group over time for the weekly average and the change from baseline in weekly average, as well as morning weekly average and evenings weekly average. Summaries will be descriptive statistics including N, mean, SD, median and range.

4.2.4.7 Analysis of fractional exhaled nitric oxide (FeNO)

FeNO is measured using the NIOX Vero® device every other day as well as at clinical visits.

For the purposes of summary and analysis, a weekly average FeNO will be computed.

Weekly FeNO will be analysed longitudinally, using MMRM as described in [Section 4.2.4.2](#).

*Weekly average in FeNO_{ijk} = Treatment group_i + baseline FeNO_k + week_j + treatment_i*week_j + random patient effect_k + covariates_k; (where i=treatment group, j=week and k=patient).*

Results will be presented for each timepoint and overall in terms of LSMEANS, treatment differences in LSMEANS, 95% CI and p-values.

Summary statistics for FeNO will be produced by treatment group over time for the weekly average and the change from baseline in weekly average. Summaries will be descriptive statistics including N, mean, SD, median and range.

4.2.4.8 Time to moderate or severe exacerbation

The null hypothesis, that the time to moderate or severe exacerbation is not different between AZD1419 and placebo groups, will be tested using the log rank test (with Kaplan Meier plot) as discussed in [Section 4.2.4](#).

A Cox proportional hazard model will be fitted to the data using the SAS[®] procedure PROC PHREG, results of the analysis will be summarized as hazard ratio, 2-sided 95% CI and p-values comparing AZD1419 with placebo. The hypothesis test will be 2-sided, with $\alpha=0.05$.

Time to moderate or severe exacerbation will be censored at 52 weeks for patients who do not experience loss of asthma control during the 52-week study period.

For patients who withdrew from the study without reporting moderate or severe exacerbation, time will be censored at the date of withdrawal, if known, else at the patients last clinical visit plus one day.

The assumptions underlying the statistical model will be explored. If the proportional hazards assumption does not hold, then alternative strategies will be considered as described in [Section 4.2.4](#).

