8.5.5 Analysis of the secondary variable(s)

8.5.5.1 Time to first moderate or severe exacerbation

Moderate and severe asthma exacerbation is defined in Section 5.1.3. Only exacerbations that are classified as moderate or severe will be analysed.

The null hypothesis, that the time to first moderate or severe exacerbation is not different between AZD1419 and placebo groups, will be tested using the log rank test (with accompanying Kaplan-Meier plot).

Time to first moderate or severe exacerbation will be censored at 52 weeks for patients who do not experience loss of asthma control during the 52-week study period.

For patients who withdraw from the study without reporting moderate or severe exacerbation, time will be censored at the date of withdrawal, if known, else at the patient's last clinical visit plus one day.

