1.2 Study design

This is a randomised, double blind, placebo-controlled Phase 2a study designed to assess the efficacy and safety of 13 once weekly doses of inhaled AZD1419 administered to patients with eosinophilic asthma controlled on a maintenance treatment of Inhaled Corticosteroids (ICS) plus a Long-acting Beta Agonist(s) LABA but no other controller medication.

This study is a multi-centre study conducted at 16 centres in 4 countries.

Prior to randomisation patients will undergo an approximately 2-4 weeks screening period. Eligible patients will be prescribed their usual controller medication (i.e. ICS + LABA in separate inhalers, in addition to a rescue medication inhaler (short-acting B2 agonist [SABA]), and issued electronic diaries, peak flow and FeNO meters to record asthma symptoms and lung function during each morning and evening at home. Asthma control will be assessed using the 5-item asthma control (ACQ-5) and when patients have shown to be controlled (ACQ-5 ≤ 0.75) they are randomised to receive AZD1419 or placebo administered as an inhalation at the clinic once per week.

A withdrawal design will be used where the first 6 doses of investigational product (IP) will be administered as add-on to the patient's regular ICS + LABA medication. The controller

medication will then be tapered down and discontinued during the next 3 doses of IP, and the last 4 doses will be administered during a period of complete ICS and LABA withdrawal (see [Figure 1](#)). In addition the study drug dose level will be adjusted using an adaptive dosing scheme (defined in [Section 4.2.2](#) of the protocol) based on appearance of flu-like symptoms. The primary endpoint is loss of asthma control, defined in [Section 1.1.1](#). When a patient meets the primary endpoint, the patient will resume ICS + LABA and will be followed for an additional 4 weeks before discontinuing the study.

The total duration of patient participation will be up to 56 weeks. Prior to randomisation patients will undergo an approximately 2-4 week screening period, which is then followed by a 12 week dosing period and an up to 40 week observation period following the last dose. The study design is presented in [Figure 1](#). The schedule of trial procedures is presented in Table 1 of the CSP.

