3.3.4 Time to moderate or severe exacerbation

Severe exacerbation is defined as a worsening in asthma symptoms and

- Use of systemic corticosteroids for at least three days and/or
- An unscheduled visit or emergency room visit due to asthma symptoms that requires at least one dose of systemic corticosteroids and/or

- An in-patient hospitalization due to asthma requiring at least one dose of systemic corticosteroids.

Moderate exacerbation is defined as a temporary increase in maintenance therapy in order to prevent a severe event supported by a sustained (≥ 2 day) worsening in at least one key control metric i.e. asthma score, reliever medication use, night time awakening or morning PEF.

The start and stop dates of severe exacerbations experienced by a patient during the treatment period will be derived from the following rule.

- The start date of a severe exacerbation is defined as the start date of systemic corticosteroids or increased use of systemic corticosteroids or of emergency room visit or hospital admission, whichever occurs first.
- The stop date is defined as the last day of systemic corticosteroids/increased use of systemic corticosteroids or hospital discharge, whichever occurs last.

The start and stop dates of moderate exacerbations experienced by a patient during the treatment period will be derived from the following rule.

- The start date of a moderate exacerbation is defined as the first day of increase in temporary maintenance therapy.
- The stop date is defined as the last day of this treatment.

The EXACA module of the eCRF will be used to derive the severe exacerbation variable. The MED1 module of the eCRF will be used to derive the moderate exacerbation variable.

Time to a moderate or severe exacerbation will be censored at 52-weeks for patients who do not experience a moderate or severe exacerbation during the 52-week study period or at the time point after which a moderate or severe exacerbation experience could not be assessed (for lost-to-follow-up patients). For patients who withdraw from the study without reporting a moderate or severe exacerbation, time will be censored at the date of withdrawal, if known, else at the patient's last clinical visit plus one day.

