As defined for the primary analysis, exacerbations that occur after a subject has discontinued IP but before maximum follow-up time will still be accounted when deriving the total number of exacerbations. Likewise, the follow-up time will reflect the follow-up time regardless of whether or not the subject is still on IP.

3.3.5 Proportion of subjects with 1 moderate or severe exacerbation during 52-weeks of treatment

The proportion of patients who experience 1 moderate or severe exacerbation during the 52-weeks of treatment will be a supportive measurement to the primary objective. The outcome variable will categorize each patient as having one moderate or severe exacerbation experience being met or not (yes=1/no=0).

The proportion of such patients will be calculated for each treatment group as:

Number of patients with 1 moderate or severe exacerbation during the 52-week treatment period/ number of patients in treatment group

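### The 52-week censoring rule for time to exacerbation names the wrong event in SAP 4.2.4.8 and protocol 8.5.5.1, and no exacerbation rule names the planned exit after loss of control

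*SAP*

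**What the plan says.** Protocol 8.5.5.1 sets the rule: "Time to first moderate or severe exacerbation will be censored at 52 weeks for patients who do not experience loss of asthma control". SAP 4.2.4.8, the analysis section, repeats it: "Time to moderate or severe exacerbation will be censored at 52 weeks for patients who do not experience loss of asthma control". SAP 3.3.4, which derives the variable, uses another condition: "Time to a moderate or severe exacerbation will be censored at 52-weeks for patients who do not experience a moderate or severe exacerbation".

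There are further clauses for early leavers. SAP 3.3.4 states: "For patients who withdraw from the study without reporting a moderate or severe exacerbation, time will be censored at the date of withdrawal". SAP 4.2.4.8 has the matching sentence: "For patients who withdrew from the study without reporting moderate or severe exacerbation, time will be censored at the date of withdrawal". Both fall back on the last clinic visit plus one day. SAP 3.3.4 also censors patients lost to follow-up at the point when the event can no longer be assessed, and adds that "the follow-up time will reflect the follow-up time regardless of whether or not the subject is still on IP".

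Under SAP 1.2, a patient who loses control resumes ICS + LABA and "will be followed for an additional 4 weeks before discontinuing the study". None of the exacerbation rules names this exit. Protocol 8.1, in a remark on the primary analysis, treats patients who lose control as withdrawn from the study. SAP Section 6 reports that the time-to-event analysis of exacerbations was clarified, but the two conditions still differ.

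**The concern.** There are two separate faults.

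1. **Wrong conditioning event.** Loss of control and exacerbation are different outcomes. A rule for exacerbation time that depends on loss of control can assign a censoring time to a patient who had the event.
2. **Unnamed exit.** Leaving 4 weeks after loss of control is part of the design, so it is neither clearly loss to follow-up nor clearly withdrawal. If a programmer applies the first limb of SAP 3.3.4 to these patients, they are counted as event-free to Week 52 without having been observed.

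The planning assumptions put this exit at twice the frequency on placebo. Any unobserved event-free time would therefore go mostly to placebo and push the hazard ratio against AZD1419. The log-rank test, Cox model and p-value for this endpoint would then depend on which sentence was programmed.

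**Working it through.** **1. The rules side by side.**

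| Patient | SAP 4.2.4.8 and protocol 8.5.5.1 | SAP 3.3.4 |
|---|---|---|
| No loss of control, no exacerbation, completes | 52 weeks | 52 weeks |
| No loss of control, moderate exacerbation | Literally 52 weeks; event dropped | Event |
| Loss of control, exacerbation observed | Event | Event |
| Loss of control, no exacerbation, planned exit | Outside the 52-week sentence; exit if counted as withdrawn, otherwise no rule | Exit if counted as withdrawn, otherwise 52 weeks |

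Row 2 is possible. A moderate exacerbation needs a temporary increase in maintenance therapy with at least 2 days of worsening in one control metric. It needs neither a 30% fall in morning PEF nor six extra puffs. Severe exacerbations are hardly exposed, because an exacerbation requiring systemic corticosteroids is itself a loss-of-control criterion. In row 4, extra time can come only from SAP 3.3.4.

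**2. The plan's own figure.** The documents give no figure for the exacerbation endpoint. For the primary endpoint, SAP 1.3 assumes 20% v 60% controlled at Week 52, so HR = ln 0.60 / ln 0.20 = 0.317. The Schoenfeld formula at two-sided 0.05 and 90% power gives 4 × (1.960 + 1.282)² / (ln 0.317)² ≈ 32 events. With 32 events the power is 90.1%. The stated figure reproduces, so 80% v 40% losing control is the right planning input. This point does not affect that figure.

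**3. Unobserved time if row 4 is set to 52 weeks.** Assume a constant hazard λ of loss of control from Week 6 and exit 4 weeks later.

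- Placebo: λ = −ln 0.20 / 46 = 0.0350 per week. Active: λ = −ln 0.60 / 46 = 0.0111 per week.
- Unobserved weeks per randomised patient = 42 − (1 − e^(−42λ)) / λ, where 42 = 52 − 4 − 6. This gives 20.0 on placebo and 8.4 on active.
- Per patient who lost control: 20.0 / 0.8 = 25.0 weeks on placebo and 8.4 / 0.4 ≈ 21.1 on active.
- Share of the credited 52 weeks: 38% on placebo and 16% on active. With 35 per arm this is about 700 and 295 patient-weeks.

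Starting the hazard at Week 0 or Week 9 instead widens the range per patient who lost control to 23-29 weeks on placebo and 20-24 on active. These are upper limits, because a patient with an exacerbation before exit is not credited.

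**4. Effect on the test.** The trial was simulated with 81 patients (SAP 1.3) and the loss-of-control model above. The documents give no exacerbation rate, so 0.5, 1.0 and 1.5 per patient-year are assumptions. Exacerbations are taken as independent of loss of control, and no loss of control is itself counted as an exacerbation. Two independent runs gave:

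| | Censored at actual exit | Credited to 52 weeks |
|---|---|---|
| HR when the true HR is 1 | about 1.0 | 1.27-1.35 |
| Two-sided error | about 5% | 11-15% |
| HR when the true HR is 0.5 | 0.50-0.51 | 0.65-0.69 |
| Power at true HR 0.5, by rate | 31-32 / 47-51 / 58-60% | 12-13 / 18-19 / 24-25% |

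Nearly all of the excess error is toward harm. A separate large-sample Cox model, with onset at Week 0, 6 or 9 and a 52-week exacerbation risk of 10-50%, gave 1.34-1.48 in place of a null HR.

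**5. Overlap of the two outcomes.** Let a share of losses of control be counted as exacerbations. At 0.5 to 1 exacerbation per patient-year, the HR with crediting to 52 weeks divided by the HR at observed follow-up was:

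| Share counted | 0% | 25% | 50% | 75% | 100% |
|---|---|---|---|---|---|
| Ratio | about 1.35 | 1.28 | 1.19-1.20 | about 1.1 | 1.00 |

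**The case against.** A reader might infer that the plan censors everyone at 52 weeks regardless of follow-up, and so biases this endpoint against AZD1419. The documents do not support that.

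- SAP 3.3.4 has a lost-to-follow-up limb, a withdrawal clause and a statement that follow-up time counts whether or not the patient is still on IP. The evident intent is actual follow-up.
- Protocol 8.1 treats patients who lose control as withdrawn, and SAP 1.2 has them discontinuing the study. On that label the withdrawal clauses censor them at exit, and the unobserved time is zero.
- The sentence in SAP 4.2.4.8 gives these patients no extra time, because it covers only patients who keep control.
- Simulating exacerbations independently of loss of control is an extreme. Loss of control triggers resumption of ICS + LABA, and SAP 3.3.4 derives moderate exacerbations from the medication module. Many losses of control may therefore be recorded as exacerbations.
- The literal reading that drops an event is strained, since censoring normally presupposes no event, and SAP 3.3.4 says so.

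All of this stands as a limit on the size. It does not remove the contradiction between SAP 4.2.4.8 and SAP 3.3.4. Nor does it give an explicit rule for the planned exit: the remark in protocol 8.1 concerns the primary analysis and is not repeated in the exacerbation rules. The documents also do not settle whether resuming usual controller treatment counts as a temporary increase in maintenance therapy.

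**Conclusion.** The rule is wrong as written; severity moderate, for one secondary endpoint. SAP 4.2.4.8 and protocol 8.5.5.1 condition 52-week censoring on the wrong event and conflict with SAP 3.3.4. The planned exit after loss of control has no explicit censoring time.

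The numerical effect runs from nil to a conditional worst case. It is nil if these patients are treated as withdrawn. If SAP 3.3.4 is read as crediting them to Week 52, a null HR becomes about 1.3, two-sided error about 10-15%, and a true HR of 0.5 is estimated at about 0.67. That rests on 80% v 40% losing control, exit 4 weeks later, assumed rates of 0.5 to 1.5 exacerbations per patient-year, and independence of the two outcomes. It shrinks to nil as more losses of control are themselves counted as exacerbations.

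The primary endpoint, sample size and safety analyses are not touched. The direction is against AZD1419, so this would not create a false efficacy claim.

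**What to change.** In SAP 3.3.4, SAP 4.2.4.8 and protocol 8.5.5.1, delete the loss-of-control condition and state one rule: patients without a moderate or severe exacerbation are censored at the earliest of Week 52, actual study exit (including the planned exit 4 weeks after loss of control), or the last date assessed for exacerbation.

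The cost is one sentence in each section and no new data. It should be settled before unblinding, so that the choice between readings cannot depend on results. Exit after loss of control may be related to exacerbation risk, so a short sensitivity analysis treating it as a competing event would be a useful but optional addition.

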4.2.4.9 Proportion of patients with a moderate or severe asthma exacerbation

The proportion of patients with an asthma exacerbation will be compared between the two treatment groups at each clinical visit, using a generalized linear model based on a generalized estimating equations (GEE) approach as described in [Section 4.2.4.1](#), with occurrence of exacerbation since the start of treatment as a binary outcome variable.

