8.5.5.2 Proportion of patients with ≥ 1 moderate or severe asthma exacerbation

The proportion of patients with ≥ 1 asthma exacerbation will be compared between the two treatment groups at each clinical visit, using a generalized estimating equation (GEE) approach, with occurrence of any exacerbation since the start of treatment as a binary outcome variable.

Summary statistics will also be presented for each treatment group at each visit.

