4.2 Analysis methods

4.2.1 Patient disposition, demography data and patients characteristics

Patient disposition will be summarized using the All Patient analysis set.

The number of enrolled patients will be summarized. The number and percentage of patients within each treatment group will be presented by the following categories; randomised, not randomised (and reason), received study treatment, did not receive study treatment (and reason), completed treatment, discontinued treatment (and reason), completed study, and discontinued study (including reason).

The number and percentage of patients, who discontinued IP, but remained in the study will be presented by treatment group. Kaplan-Meier plots will be produced summarizing the time (in days) to discontinuation of IP and withdrawal from the study.

Demographic data such as age, gender, race and ethnicity will be summarized by treatment group for the FAS.

Various baseline characteristics will also be summarized by treatment for the FAS. These include weight, height, body mass index (BMI), medical, surgical and respiratory disease histories, history of allergic rhinitis, FEV₁ (pre and post-BD) at baseline, age at onset of asthma, asthma duration, the number of asthma exacerbations in the previous 12 months, the number of asthma exacerbations requiring hospitalizations in the previous 12 months, number of exacerbations resulting in antibiotic treatment, type of recent exacerbations, the number of admissions to ICU (Intensive Care Unit) for asthma during the hospitalization, eosinophil count, smoking status, nicotine consumption, reversibility test.

The following covariates are deemed to be of interest for inclusion in the statistical models of the primary and secondary endpoints. Possible covariates include but are not limited to: age at first asthma allergy status, whether hospitalized within the last year, race, sex, baseline spirometry variable measurements, baseline PEF, baseline ACQ-5 and baseline asthma symptom scores. For Blinded Deliverable review analyses, the following five covariates have been selected: age, race, sex, age at first asthma allergy status and whether hospitalized within the last year. For the final analysis, only age and gender will be included as covariates in the statistical models.

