4.2.4.1 Loss of asthma control as group proportions

The proportion of patients with loss of asthma control will be compared between the two treatment groups at each clinical visit, using a generalized linear model based on a generalized estimating equations (GEE) approach, with occurrence of any loss of control as a binary outcome variable. Treatment group and visit will be included as factors in the model. The covariates for inclusion in the statistical model are described in Section 4.2.1. If a patient had

a ‘loss of asthma control’ event at one visit, the subsequent visits information should be removed. Each patient can only be counted once towards ‘loss of asthma control’.

This analysis will be carried out using a log-binomial regression model using PROC GLIMMIX in SAS with a random subject effect. The estimated treatment effect (i.e. the rate ratio of AZD1419 versus placebo), corresponding 95% confidence interval (CI), and two-sided p-value for the rate ratio will be presented.

In the case that If the GEE model fails to converge, due to the estimation method not being Restricted Maximum Likelihood (REML), then only the Mixed Model will be explored. The variance-covariance will be assumed to be unstructured. other options will be explored e.g. using the PROC GLIMMIX procedure in SAS. For PROC GLIMMIX, initially this will be fitted with a random statement fitting a random intercept and a Laplace approximation for maximum likelihood estimation. Again, to facilitate convergence, one or more of the covariates could be removed leaving the basic model. In case this model also fails to converge, the random statement will be removed which will result in a conventional logistic regression model being fitted.

The assumptions underlying the statistical model will be explored. If assumptions do not hold, then alternative strategies will be considered.

Summary statistics will also be presented for each treatment group at each visit.

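### The last-resort model for the exacerbation proportion treats repeated cumulative visit records on one patient as independent, and the SAP does not say whether visits after the event are kept

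*SAP*

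**What the plan says.** Protocol 8.5.5.2 asks for a GEE comparison at each clinic visit "with occurrence of any exacerbation since the start of treatment as a binary outcome" variable. SAP 4.2.4.9 keeps that outcome, "with occurrence of exacerbation since the start of treatment as a binary outcome variable", and takes its method from SAP 4.2.4.1.

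Section 4.2.4.1 sets out a chain:

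1. The model terms are fixed: "Treatment group and visit will be included as factors in the model". SAP 4.2.1 adds that "For the final analysis, only age and gender will be included as covariates in the statistical models".
2. The approach is called GEE, but the fit is a random-effects model: "This analysis will be carried out using a log-binomial regression model using PROC GLIMMIX in SAS with a random subject effect".
3. If that fails to converge, GLIMMIX is used again, and "initially this will be fitted with a random statement fitting a random intercept and a Laplace approximation for maximum likelihood estimation".
4. Covariates may then be dropped.
5. If the model still fails, "the random statement will be removed which will result in a conventional logistic regression model being fitted".

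No robust or clustered variance is named for step 5. Section 4.2.4.1 also removes a patient's visits after a loss-of-control event and counts each patient once. Section 4.2.4.9 neither repeats nor waives that rule for exacerbations.

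**The concern.** A cumulative yes/no outcome never returns to no. Once a patient has had an exacerbation, each further visit repeats the same fact. A model with a patient effect, or a GEE with robust variance, allows for this. Ordinary logistic regression does not: it counts each visit record as a new patient, so the standard error of the treatment effect is too small and the nominal 5% test rejects too often.

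The same step also changes the estimate. Section 4.2.4.1 promises a ratio of AZD1419 to placebo from a log-binomial model; conventional logistic regression gives an odds ratio.

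At stake is a secondary efficacy comparison that could be reported as significant on the strength of duplicated records.

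**Working it through.** **The plan's own figure.** The documents give no error rate for this step. The only reference value is the two-sided 5% level for tests other than the primary (Protocol 8.1; SAP 4.1 also makes them two-sided). As a calibration check, a simulated comparison at Week 52 alone, with one record per patient, rejects in 4.6% of trials with no treatment effect.

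**Inputs from the documents**
- Patients: 81 randomised, about 70 planned (SAP 1.3), allocated 1:1 (Protocol 3.5).
- Visits: Weeks 1-13, 16, 20, 28, 36, 48 and 52, which is 13 + 6 = 19 post-baseline visits (SAP Appendix A, Table 6).
- Drop-out: 10-15% (SAP 1.3); 12.5% used.
- Exit: 4 weeks after loss of control (SAP 1.2).

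**Assumed, because not given:** exacerbation risk by Week 52 of 20-80%, with constant hazard from Week 0 or from Week 6; or risk of 30% or 60%, with events clustered soon after Week 6.

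**Test.** Logistic regression on treatment and visit as factors, model-based standard error, reject if |estimate/SE| > 1.96. Arms identical; 1,500 to 2,000 simulated trials per cell of the table.

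| Records after the first exacerbation | Constant hazard from Week 0 | Constant hazard from Week 6 | Clustered after Week 6 |
|---|---|---|---|
| Kept at every visit to Week 52 | 52-57% | 44-46% | 50-55% |
| Kept for 4 weeks | 21-26% | 15-22% | 26-30% |
| Removed | 3.2-5.7% | 4.2-5.6% | 4.5-5.7% |

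**Variations**
- Age and sex added (600 trials, 60% risk): 46%, 21% and 5.3% for the three rows.
- Every loss of control ends follow-up at 4 weeks, and 25-90% of these are exacerbations: 16-19%.
- Exacerbation risk 15-40% and loss of control 60%, both assumed: 16-32% with the 4-week exit, 40-54% with carry-forward, about 1-8% with removal.
- Only an evaluation visit and one visit at 4 weeks after loss of control, i.e. weekly visits stop: 6-17%.

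**What these rates imply.** If the standard error is too small by a factor k, the rejection rate is 2[1 − Φ(1.96/k)]. Solving for k:
- 15%: k = 1.96/1.44 = 1.36
- 30%: k = 1.96/1.036 = 1.89
- 40%: k = 1.96/0.842 = 2.33
- 55%: k = 1.96/0.598 = 3.28

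**Why the range is wide.** The number of positive records after the event drives the result. During weekly dosing visits, a 4-week tail adds about four of them; after Week 16 the visits are 4 to 12 weeks apart and it adds about one.

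**The case against.** **The removal rule may carry over.** Section 4.2.4.9 adopts the method of 4.2.4.1, which removes post-event visits. The amendment history says that only one moderate or severe exacerbation per patient will be captured, and SAP 3.3.5 defines a single yes/no per patient. On that reading the model is a discrete-time hazard model and there is no inflation. This part stands as a possible reading. Against it, the rule is written for loss of control, and removing visits contradicts a cumulative outcome. The amendment history also records that the corresponding phrase was taken out of 4.2.4.1 on 14 August 2018, while 4.2.4.9 was edited twice afterwards and still has it. The SAP is ambiguous, not clearly safe.

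**Few records can follow an event.** A severe exacerbation requires systemic corticosteroids, which is itself a loss-of-control criterion, so the patient leaves 4 weeks later. This stands, and it is why a reader should not infer up to 19 dependent records per patient as the usual case. It is less complete for moderate exacerbations, which are derived from a different eCRF module and have no exit rule of their own. If they are timed separately from loss of control, the rate moves into the carry-forward range (52-56% in one set of runs).

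**The step may never be reached.** It comes last, after three other attempts, and 4.2.4.1 also allows alternative strategies if assumptions fail. This stands, and the chance of reaching it has not been estimated. A log link that lets probabilities exceed 1 is no argument at the penultimate step: if deleting the random statement leaves a logistic model, the link is already the logit there. An outcome that only moves from no to yes within a patient may still make the random-intercept fit difficult, but that has not been shown.

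**Consequences are limited.** This is one secondary endpoint without multiplicity control, and 4.2.4.8 tests the same events by log-rank and Cox with one time per patient. This stands.

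**Conclusion.** The rule in the last step is wrong for the outcome that 4.2.4.9 defines. If visits after the first exacerbation are kept, as the cumulative wording implies, the nominal 5% test rejects in roughly 15-30% of null trials when records stop 4 weeks after loss of control, less if weekly visits also stop, and in about 40-55% when records continue to Week 52. If post-event visits are removed, the rate is about 5%.

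These figures rest on assumed exacerbation rates and timing and on identical arms.

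A reader might infer a single error rate, such as 35%. The documents do not fix one: values of 36-38% appeared with full carry-forward restricted to the seven visits from Week 13 to Week 52, which is one scenario among several. Nor do they support saying that a false positive is likely, or that one convergence failure leads straight to this model. The effect is conditional on repeated non-convergence and confined to this secondary analysis.

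**What to change.** Two changes:

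- **SAP 4.2.4.1, last step, as used by 4.2.4.9.** Replace ordinary logistic regression by a GEE with independence working correlation, patient as cluster and small-sample-corrected robust standard errors. Keep the log link, with a Poisson working model and robust standard errors if the log-binomial fit fails, so that a ratio of proportions is still reported. The correction matters at this sample size: under the null, uncorrected robust standard errors rejected in 6-11% of simulated trials and bias-corrected ones in 4.8-7.1%.
- **SAP 4.2.4.9.** State whether visits after the first exacerbation are kept. If they are removed, reword the outcome, because the model then describes new events among patients still event-free and not a cumulative proportion.

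The cost is a sentence or two in the SAP and one procedure option (a REPEATED statement in PROC GENMOD or the EMPIRICAL option in PROC GLIMMIX). No data collection changes.
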